9.3.2 Serum and plasma complement levels

Serum (C3 and C4) and plasma (C3a and C5a) complement variables will be listed by dose arm and visit including changes from Baseline. Descriptive summaries (including n, arithmetic mean, median, SD, minimum and maximum) will be presented by dose arm and visit for both absolute values and changes from Baseline.

Mean and mean change from Baseline values will be plotted over time by dose arm with all dose arms overlaid on the same plot and separate plots for each variable.

Any values are that BLQ or ALQ will be handled as described in [Section 4.2.4](#).

All analyses described in this section will be performed on the FAS.

9.3.3 Serum biomarkers

Serum safety biomarkers [REDACTED] and BAFF will be listed by dose arm and timepoint including changes from Baseline. Descriptive summaries (including n, arithmetic mean, median, SD, minimum and maximum) will be presented by dose arm and timepoint for both absolute values and changes from Baseline.

Mean and mean change from Baseline values will be plotted over time by dose arm with all dose arms overlaid on the same plot and separate plots for each variable.

Any values are that BLQ or ALQ will be handled as described in [Section 4.2.4](#).

All analyses described in this section will be performed on the FAS.

9.3.4 Anti-drug antibodies

Immunological variables will be analyzed for all subjects in the SS. Anti-UCB7665 antibody data will be summarized at each scheduled visit, and the rate of ADA positive subjects will be calculated.

A calibrator screening assay measures ADA as relative mass units (RMU) in units/mL. A cut point will be determined by the bioanalytical laboratory that will be used to determine the status of ADA as above the cut point (ACP) or below the cut point (BCP). The RMU result from the calibrator screening assay will be used to report ADA levels.

For any ADA levels that are ACP, a further confirmatory assay will be performed, the results of which will be determined as either 'confirmed positive' (CP) or 'not confirmed positive' (NCP).

The results for the ADA measurements will be listed by treatment group and time point based on the SS, including the screening assay, confirmatory assay and level in units/mL.

The following definitions will be applied:

- An ADA status of positive will be concluded for any subject with an ADA level that is ACP and CP at any time point
- An ADA status of negative will be concluded for any subject with an ADA level that is either BCP or ACP and NCP at any time point
- A subject will be classified as having ADA positivity at Baseline if the Day 1, predose result is ACP and CP
- A subject will be classified as having treatment-emergent ADA positivity when meeting one of the following criteria:
 - The Baseline result is either BCP or ACP and NCP, and at least one post-Baseline time point is ACP and CP
 - The Baseline result is positive (ACP and CP) and at least one post-Baseline measurement shows a pre-defined fold increase in units/mL from the Baseline value (the fold increase from Baseline required to meet this criterion will be defined with the development of the assay and will be included in the TFLs)
- A subject will be classified as overall positive if at least one post-Baseline measurement is ACP and CP (this includes subject who have negative results at Baseline)
- A subject will be classified as overall negative if at all post-Baseline visits the ADA status is negative (this includes subjects who have positive [ACP and CP] results at Baseline)
- Inconclusive: pre-ADA negative or pre-ADA positive subjects with negative ADA samples post baseline for which time matched drug levels are above the demonstrated drug tolerance characteristics of the ADA screening assay at one or more sampling time points

- Missing: relevant samples are missing

The ADA status (positive/negative) will be summarized as a categorical endpoint (number and percentage of subjects) for all time points and overall, based on the SS.

In addition, the first occurrence of treatment-emergent ADA positivity (based on the definitions above) will be summarized (number and percentage of subjects) at each post-Baseline visit, based on the SS. This tabulation will count the number of subjects at each post-Baseline visit who fulfill at least one of the above defined criteria for treatment-emergent positivity; subjects will be counted in the numerator based on the earliest visit at which one of these criteria is fulfilled. At other visits, subjects will be counted in the denominator (assuming a measurement is available). For all tabulations, percentages will be based on the number of observations at each visit.

A separate listing will be presented (based on the SS) showing the UCB7665 concentrations and ADA measurements in the same output in adjacent columns. The listing will include the UCB7665 concentration, ADA status (ACP or BCP) and confirmatory assay results if applicable (NCP or CP), together with the units/mL for results that are CP. In addition the time since the previous administration of IMP will be reported (in days).

Finally, individual subject plots (based on the SS) will be presented displaying the ADA units/mL and UCB7665 concentrations overlaid on the same figure. The figure will also show the timing and dose of each administration of UCB7665 received during the study.

The rules for handling values that are BLQ in the UCB7665 concentration data are described in [Section 4.2.5](#) For the ADA data, any negative results for which there are no units/mL available at a specific visit will be substituted with 0.001 for the purpose of the figure.

9.3.5 Cytokines

Cytokines will be obtained at Baseline in all subjects and at subsequent visits only in subjects experiencing severe infusion reactions (or due to DMC's or sponsor's request). Only for subjects for whom additional measurements were obtained the results of the cytokine assessments will be listed by dose arm and timepoint including changes from Baseline.

If appropriate (i.e., sufficient data are available), summaries will be presented by dose arm and timepoint for both absolute values and changes from baseline. Depending on the availability of data, it may be also decided to summarize the data overall without stratification by dose arm.

A minimum of 5 subjects per dose arm with any post-dose cytokine measurements will be required in order to produce summaries by dose arm. Similarly, a minimum of 5 subjects across all dose arms with any post-dose cytokine measurements will be required to produce the summaries without stratification by dose arm.

The cytokines to be measured are presented in [Section 13.4](#).

All analyses described in this section will be performed on the FAS.

10 SAFETY ANALYSES

All safety analyses will be presented using the SS. Listing will be presented by dose arm and subject; tabulations will be presented by dose arm and overall (AE data only), with the lowest dose per kg presented first and continuing in ascending order.

10.1 Extent of exposure

All drug administration details (including date, start and stop time of infusion, location of infusion site, interruptions, discontinuations [including reasons] and volume delivered) will be listed. The duration of the infusion, in minutes, will also be calculated.

The percent of planned dose administered will be calculated based on the actual volume delivered as follows:

$$\text{Percent of Planned Dose Administered (\%)} = [100 * (\text{Actual volume} / \text{Planned volume})]$$

For all subjects the planned volume is 10mL.

The overall exposure to UCB7665 will be calculated in days as follows and listed for each subject:

$$\text{Total exposure (days)} = (\text{Date of last dose} - \text{Date of first dose}) + 1$$

The planned dose regimens are as follows:

- Subjects in Dose Arm 1 will receive 5 sc doses of UCB7665 4mg/kg at 1-week intervals
- Subjects in Dose Arm 2 will receive 3 sc doses of UCB7665 7mg/kg at 1-week intervals
- Subjects in Dose Arm 3 will receive 2 sc doses of UCB7665 10mg/kg at 1-week intervals
- Subjects in Dose Arm 4 will receive 1 sc dose of UCB7665 15mg/kg
- Subjects in Dose Arm 5 will receive 1 sc doses of UCB7665 20mg/kg

The DMC may decide to modify the dosing regimen following review of emerging safety data. In this case the modified dose regimen will be considered as a new dose arm for the study.

10.2 Adverse events

Adverse events will be recorded from the time of informed consent until study completion. All AEs will be coded ([Section 3.8](#)) and will be categorized by relationship to UCB7665.

In addition, AEs will be classified according to the CTCAE Version 4.03 for severity. For any AEs where it is not possible to provide a CTCAE grading, the events will be assessed using a standard intensity classification (mild, moderate and severe). For the purpose of the tabulations all CTCAE severity classifications will be mapped to a mild/moderate/severe grade as described in the below sections. Bleeding events classified as Grade 1 or Grade 2 (based on CTCAE) will not be reported as AEs as these will be assessed and reported as part of the ITP-BAT assessments. Bleeding events classified as Grade 3 or higher, based on CTCAE, will be reported as AEs.

A TEAE is defined as any event that was not present prior the first administration of UCB7665 or any unresolved event already present before the first administration of UCB7665 that worsens in intensity following exposure to treatment. Adverse events starting before the first administration of UCB7665 or after 8 weeks following the final dose of UCB7665 will not be considered as TEAEs. Such events will be listed only.

Where dates are missing or partially missing, AEs will be assumed to be treatment-emergent. Handling of missing dates/times for classification of AEs as TEAEs is described in [Section 4.2.7](#).

The following rules will be used to assign a TEAE to a study period:

- A TEAE will be assigned to the Dosing Period for the tabulations if the start date/time of the event is at the time of or after the first administration of UCB7665 until 7 days after the final dose; for the purpose of the analysis this will be calculated as the start date/time of the final infusion plus 168 hours;
- A TEAE will be assigned to the Observation Period for the tabulations if the start date/time of the event is greater than 7 days after the final dose until 8 weeks following the final dose; events starting later than 8 weeks following the final dose of UCB7665 are not considered as TEAEs.

Adverse events with missing start date/times will be handled as described in [Section 4.2.7](#) for this classification.

The number and percentage of subjects who experience TEAEs will be summarized for each dose arm and overall. The following summaries will be presented:

- Incidence of TEAEs (overview including number and percentage of subjects with any TEAEs, serious TEAEs, discontinuations due to TEAEs, TEAEs leading to permanent withdrawal of UCB7665, related TEAEs, TEAEs with CTCAE Grade 3 and above [or rated as 'severe' for events with no CTCAE classification], and deaths; event counts will also be included)
- Incidence of TEAEs (overview as described above) during the Dosing Period
- Incidence of TEAEs by SOC, HLT and PT
- Incidence of TEAEs during the Dosing Period by SOC, HLT and PT
- Incidence of serious TEAEs by SOC, HLT and PT
- Incidence of non-serious TEAEs by SOC, HLT and PT
- Incidence of AEs of special interest by SOC, HLT and PT
- Incidence of AEs of interest by SOC, HLT and PT
- Incidence of TEAEs by relationship, SOC, HLT and PT
- Incidence of serious TEAEs by relationship, SOC, HLT and PT
- Incidence of non-serious TEAEs by relationship, SOC, HLT and PT
- Incidence of fatal TEAEs by relationship, SOC, HLT and PT
- Incidence of TEAEs by maximum relationship, SOC, HLT and PT
- Incidence of TEAEs by maximum intensity (mild, moderate and severe), SOC, HLT and PT
- Incidence of non-serious TEAEs above threshold of 5% of subjects by SOC and PT
- Incidence of non-serious TEAEs above threshold of 5% of subjects by relationship, SOC and PT
- Discontinuation due to AEs

Summary tables will contain counts of subjects, percentages of subjects in parentheses and the number of events where applicable. A subject who has multiple events in the same SOC, HLT and PT will be counted only once in the subject counts but all events will be included.

In summaries including relationship to UCB7665, the following relationship categories will be included:

- Related
- Not related

Subjects who experience the same event multiple times will be included in the most related category for tabulations by maximum relationship. Events with missing relationship will be considered as 'Related' to the UCB7665 for summary purposes but shown as missing in the data listings.

In summaries including intensity, the CTCAE categories will be summarized according to the following categories:

- Grade 1: Mild
- Grade 2: Moderate
- Grade 3: Severe
- Grade 4: Severe
- Grade 5: Severe

These will be tabulated together with the AEs that were not classified according to CTCAE criteria i.e., all Grade 1 AEs as per CTCAE criteria will be included in the 'mild' category together with those AEs classified as mild as per the 'standard' intensity classification.

Subjects who experience the same event multiple times will be included in the most severe category for tabulations by maximum intensity. Events with missing intensity will be considered as 'Severe' for summary purposes. All data will be presented as recorded in the database for the listings.

Adverse event summaries will be ordered by alphabetical SOC, alphabetical HLT within SOC and decreasing frequency of PT in the overall column for tables including event counts. For tables including only number and percentage of subjects, summaries will be ordered by alphabetical SOC, alphabetical HLT within SOC and decreasing incidence of PT within SOC in the overall column.

A listing of all AEs will be presented by subject and dose arm. The listing will include the onset date/time and outcome date/time of the event (including relative days), the AE duration, days since first dose of UCB7665, days since most recent dose of UCB7665, pattern of event, severity/intensity, relationship, action taken and outcome. In addition the listing will flag AEs that led to discontinuation, TEAEs, AEs of interest, AEs of special interest, infusion reactions, SAEs, Sampson criteria and CTCAE grade.

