2.2 Study variables

2.2.1 Safety variables

2.2.1.1 Primary safety variable

The primary safety variable is:

- Occurrence of treatment-emergent adverse events (TEAEs)

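### SAP Section 10.2 gives two incompatible rules for an adverse event that is present before dosing and worsens after it, and assigns such an event to no study period

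*SAP*

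**What the plan says.** Section 2.2.1.1 makes the occurrence of TEAEs the primary safety variable. Section 10.2 sets the collection window: "Adverse events will be recorded from the time of informed consent until study completion". Events that begin before the first infusion are therefore in the database.

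Section 10.2 then defines a TEAE in two parts. The first is an event that was absent before the first administration. The second is "any unresolved event already present before the first administration of UCB7665 that worsens in intensity following exposure to treatment". The sentence that follows reads: "Adverse events starting before the first administration of UCB7665 or after 8 weeks following the final dose of UCB7665 will not be considered as TEAEs". On what becomes of the excluded events, it adds: "Such events will be listed only".

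The same section places TEAEs in a study period. An event goes to the Dosing Period "if the start date/time of the event is at the time of or after the first administration of UCB7665", up to 7 days after the final dose. It goes to the Observation Period "if the start date/time of the event is greater than 7 days after the final dose until 8 weeks following the final dose". Both rules depend on when the event started. Neither mentions when it worsened.

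**The concern.** An adverse event that is already present and unresolved at the first infusion has a start date before that infusion. If it worsens after exposure, one sentence of Section 10.2 makes it a TEAE and the next removes it. No program can follow both, so whoever writes the TEAE flag must choose, and the SAP gives no basis for the choice.

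The primary objective is safety and tolerability, so this affects the main result. Under the exclusion sentence, an aggravation after dosing, even a serious or Grade 3 one, would be missing from the TEAE overview and from the tables by seriousness, relationship and maximum intensity. That runs against the cautious defaults elsewhere in Section 10.2: missing dates are taken as treatment-emergent, missing relationship as related and missing intensity as severe.

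**Working it through.** The plan gives no figure to reproduce, so the check compares the rules and then illustrates the scale.

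**Test case.** An adverse event has its onset after consent and before the first infusion, is unresolved at that infusion, and rises in intensity afterwards.

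1. *Inclusion limb (Section 10.2).* The event is present before dosing, unresolved, and worse after exposure. Result: TEAE.
2. *Exclusion sentence (Section 10.2).* The start date precedes the first administration. Result: not a TEAE, listing only.
3. *Dosing Period rule (Section 10.2).* It requires a start "at the time of or after the first administration of UCB7665 until 7 days after the final dose". The event started earlier. Result: not assigned.
4. *Observation Period rule (Section 10.2).* It requires a start more than 7 days after the final dose. Result: not assigned.

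Steps 1 and 2 contradict each other. Steps 3 and 4 show that settling the contradiction in favour of inclusion is not enough, because the event still could not enter the two Dosing Period tables.

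**Does other current text settle it?**

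- Section 4.2.7 imputes partial start and stop dates for classifying events as treatment-emergent. It has no rule for a date of worsening.
- Table 4-1 computes event duration from onset and outcome date/time only.
- The adverse event listing in Section 10.2 contains onset and outcome date/time and severity, but no worsening date.
- No current section says that a worsening is entered as a new event with its own start date.

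**Can such events occur?** Events are recorded from consent, and Section 3.2.1.2 gives a Screening Period of 1 to 28 days, so there is time for them to arise.

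**Illustration of scale.** Take one subject whose only candidate TEAE is a worsened pre-dose event. With n subjects in the arm, the choice of sentence moves TEAE incidence by 1/n. Planned arm sizes are from Section 2.3.

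- Dose Arms 1 and 2, n = 15: 1/15 = 6.7 percentage points.
- Dose Arms 3 to 5, n = 12: 1/12 = 8.3 percentage points.
- Dose Arms 3 to 5, n = 6: 1/6 = 16.7 percentage points.

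**The case against.** A reader might infer that the primary safety variable will in fact lose worsened events. The SAP does not support that. Two conditions are needed: the exclusion sentence must be the one programmed, and worsening must not be recorded as a new event. On the first, a programmer could fairly treat the exclusion as the general rule and the worsening limb as its exception, since the opposite reading leaves that limb with nothing to do for these events. On the second, the recording convention is commonly left to the protocol or the CRF instructions, which are not shown here, and Section 1 defers to the protocol where the SAP does not specify otherwise. If every worsening gets its own record with a post-dose start, the exclusion does no harm.

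The conflict is also narrower than it may look. Conditions that predate consent would ordinarily be medical history (Section 6.3), and may first become adverse events when they worsen, with a start after dosing. Grade 1 and 2 bleeding, an obvious pre-existing manifestation in this disease, is not reported as an adverse event at all. It is captured by the bleeding assessment tool, and bleeding is tabulated as shifts from Baseline (Section 8.2.1.1). Affected events would remain visible in the listing of all adverse events, which flags serious events and CTCAE grade. No test or threshold in the SAP depends on the TEAE rate.

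All of this limits the consequence, and the conflict remains. Defining and flagging TEAEs is the SAP's job, and here two adjacent sentences give opposite answers that no other current section settles.

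**Conclusion.** The point stands as a contradiction in the definition of the primary safety variable, together with a gap in the period rules. It concerns adverse events with onset between consent and first dose that are unresolved at dosing and worsen afterwards.

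The loss of such events from the TEAE tables is conditional, as set out above. The percentages of 6.7 and 8.3 to 16.7 points should not be read as an estimate of bias. Each is one hypothetical subject divided by a planned arm size, and each assumes that the subject has no other TEAE. The SAP gives no count of such subjects. A correction is still warranted, because the primary variable should not depend on an undocumented programming choice and the remedy costs very little.

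**What to change.** In Section 10.2, limit the exclusion to adverse events that start before the first administration and do not worsen in intensity after it. Keep the limit of 8 weeks after the final dose.

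Then state how a worsened event is dated for the TEAE flag and the period assignment, according to how the data are collected:

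- If a worsening is recorded as a new adverse event starting on the date of worsening, say so. The existing start-date rules then work unchanged.
- If a worsening date is collected within the original record, use it as the TEAE start. The SAP does not show that such a field exists, so the wording should not presuppose one.
- If no worsening date is available, count the event as a TEAE in the overall tables and assign it to the Dosing Period by default. This fits the SAP's practice of treating events with missing dates as treatment-emergent.

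The cost is a few sentences and a small change to the TEAE flag and period logic. Under Section 1, a changed definition before database lock needs a further SAP amendment. No new data are required, and TEAE counts may rise slightly compared with a program that applies the exclusion as written.

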10.3 Clinical laboratory evaluations

Laboratory data (chemistry [excluding follicle stimulating hormone, FSH], hematology, coagulation and urinalysis) and changes from Baseline (if applicable) for numeric variables will

be listed by dose arm and visit. Any laboratory measurements that are BLQ or ALQ will be handled as described in Section 4.2.2. Values outside the reference range for the numeric variables will be flagged in the listings and in addition, results considered as markedly abnormal laboratory results (CTCAE Grade 3 and above) will be listed separately. The reference ranges will also be reported in the listings.

Chemistry [excluding FSH], hematology and coagulation variables will be summarized by dose arm at each visit, for both absolute values and changes from Baseline.

Laboratory variables will be grouped according to the laboratory function panel (Table 10-1) and categorized as normal, high or low, if applicable, based on the reference range supplied by the analytical laboratory. For selected variables that are identified in Table 10-1, the change in category from Baseline will be presented in shift tables at all post-Baseline visits.

Table 10–1: Clinical laboratory measurements

Category	Panel	Variable
Serology	Serology	HIV, HBsAg, anti-HBs, anti-HBc, anti-HCV
Hematology	Red blood cell	RBC count ^a , hemoglobin ^a , hematocrit
	Platelet	Platelet ^{ab}
	White blood cell	WBC count ^a
	White blood cell differential	Absolute counts: ANC ^a , basophils ^a , eosinophils ^a , ALC ^a , monocytes ^a Percentages: neutrophils/leukocytes ^a , basophils/leukocytes ^a , eosinophils/leukocytes ^a , lymphocytes/leukocytes ^a , monocytes/leukocytes ^a .
Coagulation	Coagulation	INR ^a , prothrombin time ^a , aPTT ^a , fibrinogen ^a
Chemistry	Electrolytes	Sodium ^a , chloride ^a , potassium ^a
	Minerals	Calcium ^a , phosphate ^a , magnesium ^a
	Kidney function	BUN ^a , creatinine ^a
	Proteins	Total protein ^a , albumin ^a , α1-globulin ^a , α2-globulin ^a , β-globulin ^a , gamma globulin ^a . For all parameters except total protein, both absolute and percentage values will be reported as part of the serum protein electrophoresis.
	Liver function	AST ^a , ALT ^a , GGT ^a , ALP ^a , LDH ^a , total bilirubin ^a , direct bilirubin (if indicated)
	Lipids	Total cholesterol ^a , triglycerides ^a
	Hormones	FSH
	Other	hsCRP ^a , amylase ^a
Urinalysis	Dipstick	pH ^a , protein, glucose, ketones, urobilinogen, bilirubin, blood, nitrite, leucocytes

Category	Panel	Variable
	Quantitative	Albumin, creatinine
	Urine sediment ^c	RBC, WBC, epithelial cells, casts, crystals, yeast, bacteria, amorphous urates, amorphous phosphates
Pregnancy test		Urine HCG ^d , serum HCG ^e
Other		HbA1c

ALC=absolute lymphocyte count; ALP=alkaline phosphatase; ALT=alanine aminotransferase; ANC=absolute neutrophil count; anti-HBc=hepatitis B core antibody; anti-HBs=hepatitis B surface antibody; anti-HCV=hepatitis C virus antibody; aPTT=activated partial thromboplastin time; AST=aspartate aminotransferase; BUN=blood urea nitrogen; FSH=follicle stimulating hormone; GGT=gamma-glutamyltransferase; HbA1c=glycosylated hemoglobin; HBsAg=hepatitis B surface antigen; HCG=human chorionic gonadotropin; HIV=human immunodeficiency virus; hsCRP=high sensitivity C-reactive protein; INR=International Normalized Ratio; LDH=lactate dehydrogenase; RBC=red blood cell; TB=tuberculosis; WBC=white blood cell.

^a Shift tables will be presented for these variables.

^b Only platelet results measured at the local laboratory will be included in the safety outputs. Measurements obtained at the central laboratory will be reported as part of the efficacy analyses.

^c If indicated, based on results of urine dipstick.

^d Urine pregnancy test will be performed predose on dosing days and at the End-of-Study Visit

^e Serum pregnancy test is done at Visit 1 (Screening) and to confirm results of positive urine test if applicable.

The number and percentage of subjects with markedly abnormal laboratory results (CTCAE Grade 3 and above) will be tabulated by dose arm and laboratory variable at each visit. The criteria for identifying abnormal laboratory results are detailed in [Section 13.5](#).

Figures of mean and mean change from Baseline will be plotted over time by dose arm for all quantitative laboratory variables (with the exception of any variables measured only at Screening and/or Baseline, eg serology, HbA1c and FSH), with all dose arms overlaid on the same plot. The reference range for each variable (male and female, if applicable) will be included on the plot for absolute values. For the differential WBC counts, figures will be presented based on percentage values only.

Any additional laboratory variables not included in the outputs described previously (including pregnancy testing, FSH and serology) will be listed separately.

Finally, in order to provide a comparison between the platelet counts measured locally and centrally, a separate listing will be presented including only the observed platelet counts from each laboratory at each visit where both measurements are obtained. Difference between laboratories will also be presented.

